# REGULATORY BACKGROUND AND JUSTIFICATION FOR THE CURRENT STUDY

The intended regulatory pathway to seek clearance for the Erchonia Violet ZERONA® Z6 OTC for the intended indication is through a 510(k) submission with supportive clinical data from the outcome of this clinical study protocol.

The intended predicate device is the Erchonia ZERONA® Z6 OTC, previously FDA cleared under K162578.

The Erchonia ZERONA® Z6 OTC is currently FDA cleared under K162578 for use as a non-invasive dermatological aesthetic treatment for the reduction of body circumference. It is cleared for Over-the-Counter (OTC) use.

Preceding its clearance under K162578, the Erchonia Zerona® Z6 OTC received FDA clearance under K143007 for use as a non-invasive dermatological aesthetic treatment for the reduction of circumference of hips, waist, and thighs. K143007 was supported by the results of a Human Factors Validation and Testing Study that evaluated the lay user's ability to operate the device safely, correctly, and effectively per the instructions in the User's Manual. In that study, 22 lay user subjects administered the treatment with the Zerona® Z6 OTC to 22 client subjects. The outcome of that study demonstrated that the lay users successfully understood the information in the User's Manual and were able to follow the instructions to operate the device and administer treatments safely, correctly, and effectively. All treated subjects in that study received an active course of 6 treatments across 2 weeks administered by the lay users. The mean circumference reduction across the waist, hips and bilateral thighs for those subjects was -3.7 inches, a statistically significant finding of equivalency to the precedent prospective randomized controlled trial (RCT) evaluating efficacy of the Erchonia ZERONA® for noninvasive circumference reduction of the waist, hips, and bilateral thighs. In that prior study, 67 males and females aged 18 to 65 years received the identical treatment protocol of 6 treatments with the Zerona® equally spaced across 2 weeks to the waist, hips, and bilateral thighs. The 35 subjects who received the active laser treatment attained an average total circumference reduction of 3.5 inches compared with a mean decrease of 0.68 inches for the 32 subjects who received the sham treatment.

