### Sample Size

There will be a minimum of 22 qualified subjects enrolled in and completing this study.

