#### PRIMARY EFFICACY OUTCOME

The primary efficacy outcome for this clinical study is the mean change in combined waist-hipsbilateral thighs circumference measurement at study endpoint (following completion of the sixth and final treatment administration procedure) relative to baseline (pre-procedure).

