#### PRIMARY EFFICACY OUTCOME EVALUATION

To determine primary efficacy outcome success, the mean change across all subjects enrolled in this study in combined waist-hips-bilateral thighs circumference measurements at study endpoint relative to baseline will be calculated and compared to the relative mean change attained for treated subjects in the reference study.

As this study is a non-inferiority design, the research hypothesis is that violet diode therapy with the Erchonia Violet ZERONA® Z6 OTC is either equivalent to, or superior to, red diode therapy with the Erchonia Zerona® Z6 OTC in effecting a clinically meaningful reduction in body circumference.

The selected equivalence margin ( $\delta$ ) is ±5%. Therefore, non-inferiority will be established if the mean change in combined circumference measurement for subjects treated with the violet diode laser in the current study is no more than 5% less than the subject group who received treatment with the red diode laser in the predicate reference trial that supported efficacy of the Zerona® Z6 OTC device (K143007).

In the predicate reference study, the mean change in combined circumference measurements across the same 6-treatment 2-week evaluation period was a decrease of 3.72 inches. Therefore, success for the current study will be determined as having been met if the mean change in combined circumference measurements for the subject group in the current study is  $-3.72\pm5\%$  inches (-3.53 to -3.91 inches). This is defined as the maximally clinically acceptable difference for which the range of efficacy values ( $\pm5\%$ ) are "close enough" to be considered equivalent.

Version 1.0

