#### SUPPORTIVE SECONDARY EVALUATIONS

The following two secondary evaluations will be performed to provide direct support for the primary efficacy evaluation outcome are will therefore be assessed with respect to statistical significance of change and/or against pre-determined non-inferiority success criteria.

- (i) T-test for independent samples will be performed to compare the mean change in combined circumference measurements across study evaluation (at endpoint relative to baseline) for subjects treated with the Violet ZERONA® Z6 OTC in the current study to the relative mean change for subjects treated with the ZERONA® Z6 OTC in the reference study treatment group. i.e., between device treatment groups. A finding of the difference being not statistically significant (p>0.05) will provide statistically significant and clinically meaningful support for the equivalency of the efficacy of the two devices.
- (ii) Responder rate analysis will be conducted wherein individual responder success is defined per the reference study as at least a 3.0-inch reduction (≥-3.0 inches) in combined circumference measurements for the waist, hips, and bilateral thighs from baseline to after study treatment completion. The maximally clinically acceptable difference for which the responder rate for the current study subject group is defined is (±5%), that is, 73% +/- 5% (68% - 78%), as the responder rate attained in the reference study was 73%.

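### The responder threshold symbol (≥ -3.0 inches) contradicts the words beside it on the plan's signed-change scale; the intended rule is clear, but the symbol should be corrected

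*Combined protocol and SAP*

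**What the plan says.** Under Supportive Secondary Evaluations (ii), the combined protocol and SAP defines an individual responder by "at least a 3.0-inch reduction (≥-3.0 inches) in combined circumference measurements". The group's responder rate is then judged against a band of 68% to 78%, centred on 73% "as the responder rate attained in the reference study was 73" percent.

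The scale is set in the two sections on the primary outcome. Change is taken at endpoint "relative to baseline (pre-procedure"), so a loss of circumference is negative. The reference mean change "was a decrease of 3.72 inches", and the primary success range is written with minus signs, as "inches (-3.53 to -3.91 inches").

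The Hypotheses section uses the same signed scale. It prints μ < -3.53 for the null (inferior) and μ ≥ -3.53 for the alternative (not inferior).

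**The concern.** One definition carries two rules. The words ask for a loss of 3.0 inches or more. Read on the plan's signed scale, the symbol selects subjects who lost 3.0 inches or less, did not change, or gained. The two rules agree only for a subject at exactly -3.0.

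This is a pre-specified threshold feeding a numerical success band, so the contradiction sits in a decision rule and not in background text. A programmer who coded the symbol would count the intended non-responders and drop the intended responders. Checking the other directional formula in the plan would not help, because the alternative hypothesis points the same wrong way.

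**Working it through.** **Inputs from the documents.** Reference mean change -3.72 inches and the primary range (Primary Efficacy Outcome Evaluation); reference responder rate 73% and band 68% to 78% (Supportive Secondary Evaluations); 22 treated clients in the reference study (Regulatory Background: "22 lay user subjects administered the treatment with the Zerona® Z6 OTC to 22 client subjects"); at least 22 subjects in this study (Sample Size).

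**1. Confirm the scale.** 3.72 × 0.95 = 3.534 and 3.72 × 1.05 = 3.906. These reproduce the printed limits of -3.53 and -3.91, so reductions are negative.

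**2. Apply both rules to sample changes.**

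| Change (inches) | Words: change ≤ -3.0 | Symbol: change ≥ -3.0 |
|---|---|---|
| -5 | responder | not |
| -3.72 (reference mean) | responder | not |
| -3.0 | responder | responder |
| -0.68 (mean in the sham group of the earlier randomized trial) | not | responder |
| 0 | not | responder |
| +1 | not | responder |

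**3. Reproduce the reference rate.** The documents do not give the count. Of the possible counts out of 22, 16/22 = 72.7% rounds to 73%; 15/22 = 68.2% and 17/22 = 77.3% do not. So 16 is inferred.

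**4. See which rule fits 73%.** If the changes are symmetric about -3.72, at most half can lie at or above -3.0, so 73% cannot come from the symbol. The documents give no SD. Assuming normality, P(change ≤ -3.0) = Φ(0.72/SD):

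| Assumed SD (inches) | Words | Symbol |
|---|---|---|
| 0.8 | 81.6% | 18.4% |
| 1.19 | 72.7% | 27.3% |
| 3.0 | 59.5% | 40.5% |

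An SD of about 1.19 reproduces 16/22 under the words. No SD does so under the symbol.

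Without symmetry, the symbol reading is not strictly impossible. If 16 subjects had changes of -3.0 or above, the other 6 would have to average at most (22 × -3.72 + 16 × 3.0)/6 = (-81.84 + 48)/6 = -5.64 inches. That is a strongly skewed result which nothing in the documents suggests.

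**5. Effect if the symbol were coded.** Rate by the symbol = 100% − rate by the words + share at exactly -3.0. Ignoring ties, a device matching the reference scores 6/22 = 27.3%.

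With n = 22 the band admits 15, 16 or 17 responders (68.2%, 72.7%, 77.3%); 14 (63.6%) and 18 (81.8%) fall outside. For a true rate of 16/22, the binomial probability of 15 to 17 is 52.6% under the words. Under the symbol the rate is 6/22, and the probability is 0.0075%.

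**6. Where the call changes.** The symbol result lies in 68% to 78% when the rate by the words lies in 22% to 32%.

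| Rate by the words | Words | Symbol (complement) |
|---|---|---|
| 68% to 78% (15 to 17 of 22) | pass | 22% to 32%: fail |
| 22% to 32% (5 to 7 of 22) | fail | 68% to 78%: pass |
| for example 50% | fail | 50%: fail |
| for example 90% | fail | 10%: fail |

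**The case against.** The strongest reply is that the rule is already stated correctly in words. The symbol is a gloss in parentheses, plausibly a magnitude of at least 3.0 with a minus sign to mark a loss. The 73% rate and the -3.72 mean leave little doubt about the intent, so a careful analyst would code the words. This stands: harm arises only if the symbol is programmed. It does not make the symbol right, since that loose reading conflicts with the signed values in the primary outcome section.

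A second reply is that the slip would probably be noticed. Under Study Blinding the statistician receives both data sets with the same variables, and the inverted rule run on the reference data would return about 27% against the documented 73%. This stands in part. The plan takes 73% as a fixed benchmark and does not require the reference data to be scored again.

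A reader might infer that coding the symbol reverses the success call in general. The band does not support that. It is two-sided, so both rules fail at rates such as 50% or 90%. A reader might also infer that study success is at risk. It is not, because success rests on the mean-change criterion, which this symbol does not enter.

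**Conclusion.** The point holds as a notation error in a supportive secondary decision rule. On the plan's own scale the symbol contradicts the words, and the words are the intended rule. If the symbol were programmed, a device matching the reference would score about 27% in place of about 73%. The call would change for rates by the words of about 68% to 78% or 22% to 32%, and at no others. The primary success rule is unaffected.

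This rests on three assumptions: the count of 16/22, inferred from 73% of 22; no subjects at exactly -3.0 inches; and, for the argument that 73% fits only the words, a roughly symmetric distribution of changes. The direct contradiction between words and symbol needs none of them.

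**What to change.** In Supportive Secondary Evaluations (ii), replace the parenthetical symbol so that the definition reads: change from baseline ≤ -3.0 inches (a reduction of 3.0 inches or more). Correct the same reversal in the Hypotheses section, so that the null is μ > -3.53 and the alternative is μ ≤ -3.53, and state once that change is endpoint minus baseline with reductions negative.

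The responder correction is one symbol, and the hypotheses need one symbol each. The 3.0-inch cut-off, the 73% benchmark, the band, the sample size and the data collection stay as they are. The change should be made before the analysis is programmed.

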#### Rationale for Sample Size

Sample size is determined to be identical to the final sample size treated and evaluated in the 2014 Zerona® Z6 OTC comparative study to enable clinically meaningful statistical comparison of outcomes to be performed.

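### As written, the supportive responder band (68% to 78%) excludes better results, contrary to the study hypothesis, and ignores sampling error in both studies

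*Combined protocol and SAP*

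**What the plan says.** Under Supportive Secondary Evaluations, the SAP lists two evaluations as direct support for the primary outcome, to be judged on statistical significance and/or "against pre-determined non-inferiority success criteria". In the second, a responder has "at least a 3.0-inch reduction" in combined circumference, and the acceptable rate is "73% +/- 5% (68% - 78%), as the responder rate attained in the reference study was 73" per cent. No test, confidence interval, error rate or power is given for this comparison, and nothing says that a rate above 78% also succeeds.

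The Primary Efficacy Outcome Evaluation section states the research hypothesis as violet therapy that "is either equivalent to, or superior to, red diode therapy". Expected Results likewise treats superior results as non-inferior.

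On numbers, the regulatory background says that in the reference study "22 lay user subjects administered the treatment with the Zerona® Z6 OTC to 22 client subjects". For the current study, "There will be a minimum of 22 qualified subjects enrolled in and completing this study". The rationale is a match to the reference study, with no power calculation: "Sample size is determined to be identical to the final sample size treated and evaluated in the 2014 Zerona® Z6 OTC comparative study".

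**The concern.** A non-inferiority criterion has a lower limit only. This one has an upper limit too, so an unusually good responder result would sit outside the pre-specified range, and the sponsor would have to reinterpret the rule after seeing the data.

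The second problem is separate. A 5-point band is narrow beside the sampling error of a rate from about 22 subjects, and that error is present in both studies. Comparing the observed rate with fixed limits cannot separate a device equal to the reference from one that is materially worse. The plan keeps this evaluation apart from the descriptive-only analyses and gives it a success range, so a reader of the submission would take a rate inside the band as evidence of non-inferiority.

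**Working it through.** **Inputs.** Reference rate 73% and band 68% to 78% (Supportive Secondary Evaluations); 22 treated subjects in the reference study (regulatory background); minimum of 22 in the current study (Sample Size). The true responder rates below are assumptions, shown as a range.

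**Reproducing the plan's figures.** The documents give the 73% without a count. Of 22 subjects, 15 is 68.2%, 16 is 72.7% and 17 is 77.3%, so 16/22 is the only count that rounds to 73%. The count is therefore inferred. The band is 73 - 5 = 68 and 73 + 5 = 78, in absolute points. A relative 5% would give 73 × 0.95 = 69.35 and 73 × 1.05 = 76.65, which is not what is printed.

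**Counts in the band at n = 22.** 14/22 = 63.6% is below it; 15, 16 and 17 are inside; 18/22 = 81.8% and every higher count are above it.

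**Chance of falling in the band.** With X ~ Binomial(22, p), P(in band) = P(X=15) + P(X=16) + P(X=17). At p = 0.73 this is 0.159 + 0.188 + 0.179 = 0.526.

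| True rate | In band | Too high (18 or more) | Too low (14 or fewer) |
|---|---|---|---|
| 50% | 6.5% | 0.2% | 93.3% |
| 55% | 14.3% | 0.8% | 84.8% |
| 60% | 26.3% | 2.7% | 71.0% |
| 65% | 40.2% | 7.2% | 52.6% |
| 73% | 52.6% | 25.2% | 22.2% |
| 80% | 40.1% | 54.3% | 5.6% |
| 85% | 21.5% | 77.4% | 1.1% |
| 90% | 6.1% | 93.8% | 0.1% |

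At n = 22 a device 13 points worse than the reference (60%) meets the band more often than one 12 points better (85%).

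**Larger n.** I applied the same sum to each n from 23 to 40, over the counts x with 68% ≤ x/n ≤ 78%. At a true 60% the chance of falling in the band is 12% to 24%. At a true 73% the chance of missing it is 45% to 67%. The ordering of 60% above 85% is not universal: at n = 27 it is 16.8% against 19.6%, and at n = 40 it is 12.2% against 13.1%.

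**Uncertainty in the reference rate.** The exact (Clopper-Pearson) 95% interval for 16/22 is 49.8% to 89.3%, roughly ±20 points, against a band of ±5.

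**Dropping only the upper limit.** P(X ≥ 15) is 77.8% at a true 73% and 94.4% at 80%. It is still 47.4% at 65% and 29.0% at 60%.

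**Rule based on a confidence limit.** The Newcombe lower limit is d - √[(p₁ - l₁)² + (u₂ - p₂)²], where l₁ and u₂ are Wilson limits. Against 16/22 it is -25.2 points at 16/22, -15.7 at 18/22 and -5.3 at 20/22. For 20/22: 0.182 - √[(0.909 - 0.722)² + (0.868 - 0.727)²] = -0.053. It first clears -5 points at 21/22. At a true 73%, P(X ≥ 21) = 22 × 0.73²¹ × 0.27 + 0.73²² = 0.009. A two-group test planned for a 5-point margin, one-sided 0.025 and 80% power needs (1.960 + 0.842)² × 2 × 0.73 × 0.27 / 0.05², or 1,238 per group.

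**The case against.** The strongest reply is that the upper figure is loose equivalence notation. The SAP never says in words that a rate above 78% fails, the lead-in calls these non-inferiority criteria, and the primary section also puts its own margin one-sidedly, as a shortfall of at most 5%. That reading is possible. But the primary section then prints a two-sided success range as well (-3.53 to -3.91 inches), so the literal reading of the responder band is reasonable too and nothing excludes it. What stands is that this is a conflict within the text, not proof that the sponsor means to reject better results. The reply leaves the sampling-error problem untouched.

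A reader might infer that a clearly worse device would often pass. The figures do not support that: it is 26% at 60%, but 14% at 55% and 6.5% at 50%. What they do show is that no limit is set on the false-pass rate.

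It is also fair that 22 is a floor. The modified intent-to-treat set includes all subjects treated at least once with a valid baseline, so the analysed number could be larger. Of the sizes checked, 22 gives the highest chance at a true 60%. The main pattern remains at larger sizes, though the figures change.

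**Conclusion.** The point holds. As written, the responder band contradicts the hypothesis it is meant to support, and its false-pass rate is uncontrolled because neither study's sampling error enters the rule. With 22 analysed, an identical device misses the band 47% of the time, 25% by being too high. A device at 60% falls in the band 26% of the time and one at 85% falls in it 21% of the time.

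These figures rest on a binomial model, the assumed true rates, 22 as the analysed number, and 16/22 as the inferred reference count.

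A reader might infer that missing this band fails the trial. The documents do not support that. Primary success is defined separately on the mean change, nothing links the responder result to it, and the indication sought contains no responder claim. The consequence is a supportive criterion that cannot bear the weight given to it.

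**What to change.** Amend item (ii) of Supportive Secondary Evaluations before the data are seen:

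- Remove the 78% upper limit.
- State the reference count and denominator as well as the percentage.
- Report the responder rate with an exact 95% confidence interval, and the between-study difference with a 95% confidence interval by a named method.
- Claim responder non-inferiority only if the lower limit of that difference is above -5 points. Otherwise label the result descriptive.

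Removing the upper limit alone is not enough, since it leaves the sampling-error problem in place.

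The cost is SAP wording: no new subjects, visits or measurements. The downside should be stated openly. With about 22 subjects per study the 5-point margin is very unlikely to be met, so the responder result will almost certainly be descriptive.

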#### ADDITIONAL SECONDARY EFFICACY ANALYSIS

Additional secondary efficacy analysis will comprise descriptive only presentation of the mean, standard deviation, and range of circumference measurements (inches) for each individual treatment area of the waist, hips, and right and left thighs, separately, at baseline, and endpoint, and the change between the two assessment points, in table format. As no additional claims are intended to be supported based on the additional secondary efficacy analysis, no statistical analysis of findings will be performed.

#### INDIVIDUAL TEST SITE EFFICACY ANALYSIS

Comparison of the primary efficacy outcome of mean change in combined waist-hips-bilateral thighs circumference measurements at study endpoint relative to baseline for subjects treated in the current study with the Violet Zerona® Z6 between each of the two study test sites will be conducted to support poolability of the study results.

#### SAFETY ANALYSES

Safety analyses will be based on all enrolled subjects and will be assessed by evaluating and comparing frequency and incidence of observed and/or reported adverse events between subjects who received treatments with the Erchonia Violet ZERONA® Z6 OTC in the current study and subjects who received treatments with the Erchonia ZERONA® Z6 OTC treatment in the predicate reference study. A chi-square test with a continuity correction will be performed to compare the percentage of subjects who had adverse events between the two subject groups.

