Both the predicate and the subject laser devices have the same treatment protocol as will be evaluated for the Violet ZERONA® Z6 OTC in this current study: 6 treatments occurring over 2 weeks: 3 treatments per week; each treatment every other day.

Therefore, as usability has already been established, and all other variables of device user, use, and application are held constant, the goal of this study is solely to demonstrate that efficacy of application of violet light over 20 minutes per treatment administration procedure using the Erchonia ZERONA® Violet Z6 OTC is equivalent to application of red light over 40 minutes per treatment administration procedure using the Erchonia ZERONA® Z6 OTC with respect to reduction in body circumference attained.

The rationale for evaluating efficacy of the application of violet diodes in this current study is that prior research and preliminary testing has demonstrated that non-inferior (equivalent or superior) results with respect to body circumference reduction can be attained with application of violet light compared with application of red light using the same treatment administration protocol but with lesser treatment administration time per treatment administration – 20 minutes versus 40 minutes, respectively, which is a significant time savings to the patient.

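### Optional, low-cost improvement: the only between-group safety test, a continuity-corrected chi-square in 22 or more vs 22 subjects, has no interval beside it, cannot be computed with zero events, and is conservative.

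*Combined protocol and SAP*

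**What the plan says.** The Safety Analyses section sets the population, "Safety analyses will be based on all enrolled subjects", and the approach, "evaluating and comparing frequency and incidence of observed and/or reported adverse events", with the predicate reference study as comparator. The one inferential method follows: "A chi-square test with a continuity correction will be performed to compare the percentage of subjects who had adverse events". The section gives no significance level, no confidence interval, no fallback for zero events and no rule for reading a non-significant result. No interval is planned elsewhere in the SAP either.

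The group sizes come from other sections. In the reference study, "22 lay user subjects administered the treatment with the Zerona® Z6 OTC to 22 client subjects" (Regulatory Background and Justification for the Current Study). The Sample Size section asks for a "minimum of 22 qualified subjects enrolled in and completing this study". Since safety covers everyone enrolled, the current group is 22 or more, with no stated maximum.

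**The concern.** The results are meant to support a 510(k) submission for a device that differs from its predicate in light output and treatment time, and this is the only formal between-group comparison of safety. As planned it has three weaknesses.

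- **Information.** A p-value from about 44 subjects does not show how large a difference in adverse event rates the data leave open.
- **Computability.** With no events in either group, a foreseeable outcome, the prespecified statistic does not exist.
- **Sensitivity.** The continuity correction makes the test more conservative than it needs to be at these sizes. In a safety comparison, that makes a real difference easier to miss.

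**Working it through.** **Inputs.** From the documents: reference n = 22; current n at least 22; corrected chi-square on the percentage of subjects with adverse events. Assumed, because the documents do not give them: two-sided 0.05, the event rates shown, and a current group of 22 to 30. The plan states no power or detectable difference for safety, so there is no figure of its own to reproduce.

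**1. Zero events.** For events a of n1 and b of n2, with N = n1 + n2, the corrected statistic is

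N(|a(n2 - b) - b(n1 - a)| - N/2)² / [n1 n2 (a + b)(N - a - b)],

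with the bracket before squaring set to 0 if negative. At a = b = 0 both numerator and denominator are 0. The chance of no event at all is (1 - p)^N for a common true rate p:

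| True rate | 22 vs 22 | 30 vs 22 |
|---|---|---|
| 5% | 0.95^44 = 10.5% | 0.95^52 = 6.9% |
| 2% | 0.98^44 = 41% | 0.98^52 = 35% |

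**2. What an interval would show.**

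- *0/22 in a group.* Clopper-Pearson upper limit = 1 - 0.025^(1/22) = 15.4%. Wilson upper limit = 1.96²/(22 + 1.96²) = 3.84/25.84 = 14.9%. The Newcombe interval for 0/22 vs 0/22 is therefore -14.9 to +14.9 points.
- *2/22 vs 1/22.* Difference 4.5 points; Wilson limits 2.5% to 27.8% and 0.8% to 21.8%. Newcombe lower limit = 0.0455 - √[(0.0909 - 0.0253)² + (0.2180 - 0.0455)²] = -13.9 points. Upper limit = 0.0455 + √[(0.2781 - 0.0909)² + (0.0455 - 0.0081)²] = +23.6 points.

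**3. One table by hand, 5/22 vs 0/22.** The corrected statistic is 44 × (110 - 22)² / (22 × 22 × 5 × 39) = 340,736/94,380 = 3.61, so p = 0.057. The Boschloo p (twice the smaller one-sided p) is 0.024, and the Newcombe interval is 3.2 to 43.4 points.

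**4. All tables, 22-30 vs 22.** Every table was enumerated, and size and power were obtained from exact binomial sums. At 22 vs 22 there are 23 × 23 = 529 tables. Two are not computable (nobody has an event, everybody has one), which leaves 527. Over the nine sizes the total is 5,571.

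| Quantity | Corrected chi-square | Boschloo |
|---|---|---|
| Boschloo p above corrected p | – | 0 of 5,571 tables |
| Tables with p ≤ 0.05, 22 vs 22 | 260 | 296 (36 more) |
| Extra tables flagged per size, 22-30 | – | 28-36 |
| Flagged by corrected test only | 0 | – |
| Maximum size, 22 vs 22 | 2.3% | 4.97% |
| Maximum size, 22-30 vs 22 | 2.1%-2.7% | 4.3%-5.0% |
| Power 25% vs 5%, 22 vs 22 | 23% | 44% |
| Power 15% vs 5%, 22 vs 22 | 3.7% | 11.3% |
| Power 10% vs 2%, 22 vs 22 | 1.2% | 4.5% |

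With four or fewer events in total at 22 vs 22, neither test rejects any table.

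**5. Test against interval.** These are the tables in which the Newcombe interval and the test disagree about zero difference at 0.05:

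| Current n | Newcombe vs Boschloo | Newcombe vs corrected |
|---|---|---|
| 22 | 0 | 36 |
| 23-30 | 2-12 per size | 36-44 per size |

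Each disagreement with Boschloo has the interval excluding zero while p is above 0.05. At 5/27 vs 0/22, for example, p = 0.060 and the interval is 0.4 to 36.7 points.

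**The case against.** The case for leaving the plan alone is substantial. The corrected chi-square is a valid test. No success criterion depends on it, and the Regulatory Background section says "the goal of this study is solely to demonstrate that efficacy of application of violet light over 20 minutes". The groups are not randomised, which no choice of test repairs. The large power gain needs an assumed 25% vs 5% contrast that nothing in the documents supports. Counts of 0 vs 0 would be reported anyway, and Boschloo then returns only p = 1. All of this stands. It is why the change is optional and why the interval comes before the change of test.

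Four stronger readings are tempting, and none is supported.

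- *The planned test is an error.* It does not inflate false positives; it is only conservative.
- *The sponsor will read p > 0.05 as comparable safety.* The SAP does say "A finding of the difference being not statistically significant (p>0.05) will provide statistically significant and clinically meaningful support for the equivalency", but under Supportive Secondary Evaluations and for efficacy only. Safety Analyses is silent on the reading.
- *Boschloo is never less sensitive at any enrolment.* The check of p-values covers 22-30 vs 22. From about 59 vs 22, some tables have a Boschloo p slightly above the corrected p, although no decision changed up to 70 vs 22 at the levels checked (0.01, 0.02, 0.025, 0.05 and 0.10).
- *The new test and interval always agree.* They do so at exactly 22 vs 22. Because 22 must complete and all enrolled are analysed, one dropout already makes the current group at least 23.

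**Conclusion.** The point holds as an optional improvement, not as an error in the plan. The absence of an interval and of a zero-event rule follows from the text alone and needs no assumption. The interval is what matters most: if no events occur, it is the only output that shows a difference of about 15 points either way is still open. The gain from changing the test is real within 22-30 vs 22. It is sizeable only if events are fairly common in one group, and small in absolute terms when they are rare. The sensitivity results rest on an assumed two-sided 0.05, assumed event rates and that enrolment range.

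**What to change.** Replace the last sentence of Safety Analyses with text to this effect:

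*The percentage of subjects with adverse events will be compared with the two-sided Boschloo exact test (twice the smaller one-sided p-value, capped at 1). Each group's rate will be reported with a Clopper-Pearson 95% interval, and the between-group difference with a Newcombe score 95% interval without continuity correction. The intervals are descriptive, and a non-significant result will not be taken as evidence of comparable safety.*

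If the sponsor prefers to keep the planned test, adding the intervals and the final clause gives most of the benefit. A line should then say that with zero events only the counts and intervals are reported.

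The cost is three sentences in place of one and standard software, with no change to subjects, visits or data. There are three downsides. A safety difference becomes somewhat easier to flag. With 23-30 current subjects the interval and Boschloo can still conflict in a few tables, hence the descriptive label. Boschloo is also not uniformly stronger than Fisher's exact test: for 5% (violet) vs 25% at 23 vs 22, power is 0.429 against 0.478. Fisher is a workable second choice in this range. It too misses no table that the corrected test flags, but it adds only 8-26 tables per size.
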